3.12. Important Protocol Deviations

Important protocol deviations are defined in the Trial Issues Management Plan. A listing and a summary of important protocol deviations by treatment will be provided.

3.13. Efficacy Analyses

The primary estimand for primary endpoints and key secondary endpoints is to assess the treatment difference between tirzepatide and placebo relative to the efficacy measures for all randomized participants. The treatment policy strategy will be used to handle intercurrent events (ICEs), meaning all the observed values for the variable of interest are used regardless of whether or not the ICE occurs. The details of the primary estimand for each endpoint will be described in the following sections.

3.13.1. Primary Endpoints/Estimands Analysis

3.13.1.1. Change from Baseline in Kansas City Cardiomyopathy Questionnaire-Clinical Summary Score (KCCQ-CSS)

3.13.1.1.1. Estimand for the Endpoint

The estimand for the primary endpoint is described by the following attributes:

- Endpoint: change from baseline to Week 52 in KCCQ-CSS.
- Treatment condition of interest: tirzepatide MTD versus placebo.
- Handling of ICEs: using the treatment policy strategy to handle all ICEs.
- Population: all randomized participants.
- Population-level summary: the median difference between treatment arms.

The KCCQ is a 23-item, participant self-administered questionnaire that assesses impacts of HF "over the past 2 weeks" on 7 domains (Green et al. 2000; Joseph et al. 2013). Each of the 23 individual items are answered on Likert scales of varying length (5-point, 6-point, or 7-point scales). Domain scores are obtained by averaging the associated individual items and transforming the score to a 0 to 100 range. Higher scores indicate better health status. KCCQ-CSS is a summary score that is derived by taking the mean of the Physical Limitation and Total Symptom scores. Detailed scoring instructions are provided in Appendix 1, Section 5.1.

3.13.1.1.2. Main Analytical Approach

A stratified Wilcoxon test (van Elteren 1960) will be used as the main analysis method, controlling for the stratification factors of HF decompensation within 12 months of screening (Y/N), diagnosed T2DM (Y/N), and baseline BMI $(<35, \ge 35 \text{ kg/m}^2)$. The Hodges-Lehmann estimate for the median difference and 2-sided 99% and 95% CIs will be reported.

Missing KCCQ-CSS measurements at Week 52 will be imputed through multiple imputation as specified in Section 3.13.1.3. The complete datasets generated through multiple imputation will be analyzed and a Van Elteren test will be conducted for treatment comparison. The final statistical inference over multiple imputation will be guided by the method proposed by Rubin (1987).

The empirical cumulative distribution function and histogram of the change from baseline to Week 52 in the KCCQ-CSS will be provided by treatment group.

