9.1. Statistical Hypotheses

Two primary hypotheses will be tested in this study:

- Tirzepatide MTD is superior to placebo for the change from baseline to Week 52 in KCCQ-CSS.
- Tirzepatide MTD is superior to placebo for the occurrence of the composite endpoint of CV death and/or HF events over time.

Key secondary hypotheses (all under multiplicity control) are that tirzepatide MTD is superior to placebo with regards to

- change from baseline to Week 52 in 6MWD
- percent change from baseline to Week 52 in body weight, and
- change from baseline to Week 52 in hsCRP.

All primary and key secondary hypotheses will be tested with the overall family-wise type I error rate at a 2-sided alpha level of 0.05 through the multiplicity control approach based on the graphical multiple testing procedure. For the primary hypotheses, the HF outcome will be tested at a 2-sided alpha level of 0.04, and change in KCCQ-CSS will be tested at a 2-sided alpha level of 0.01 in parallel for statistical significance. If significant, the respective alpha of the primary endpoints will be propagated to test the key secondary endpoints. If any of the primary endpoints is not significant, then the appropriate alpha after the key secondary endpoints testing will be recycled to that primary endpoint. The detailed graphical testing scheme will be outlined in the SAP.

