9.2. Sample Size Determination

A sample size of 700 participants (350 in each treatment group) will provide roughly 80% power for the change from baseline to Week 52 in KCCQ-CSS using Wilcoxon rank sum test under the assumptions that the change from baseline to Week 52 in KCCQ-CSS follows normal distribution with mean of 5 and standard deviation of 19 in placebo and mean of 10 and standard deviation of 19 in tirzepatide group at a 2-sided alpha of 0.01 significance level. The expected events at the end of the study will provide roughly 80% power to demonstrate the superiority of tirzepatide MTD to placebo in occurrence of the composite endpoint of CV death and/or HF events at a 2-sided alpha of 0.04 significance level under the treatment effect estimate assumption of 0.5. The study power is calculated using nQuery Version 9.1.

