9.4.2.1. Change from Baseline in KCCQ-CSS

For the primary endpoint of change from baseline to Week 52 in KCCQ-CSS, a stratified Wilcoxon (Van Elteren) test will be used as the primary analysis method, controlling for the stratification factors of HF decompensation within 12 months of screening (Y/N), diagnosed T2DM (Y/N), and baseline BMI \geq 35 kg/m² (Y/N). Population-level summary of Hodges-Lehmann estimate for the median difference and corresponding confidence interval will be reported.

The last measurement prior to randomization KCCQ-CSS will be used as baseline. Missing KCCQ-CSS at Week 52 will be imputed through multiple imputations based on the reason of missingness with details described in the SAP. The statistical inference over multiple imputations will be guided by the method proposed by Rubin (1987).

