3.3. Adjustments for Covariates

The study is stratified by diagnosed type 2 diabetes mellitus (T2DM) (Y/N), HF decompensation (including hospitalization for HF requiring intravenous [IV] diuretic treatment or urgent HF visit requiring IV diuretic treatment) within 12 months of screening (Y/N), and baseline BMI group ($<35, \ge 35 \text{ kg/m}^2$). Unless otherwise specified, the stratification factors will be adjusted in the efficacy analyses. The value for stratification factors will be obtained from the data collected or derived from the electronic case report form (eCRF). In addition, the baseline value of the endpoint will be used as a covariate when appropriate.

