3.13.2.1.2. Main Analytical Approach

For the key secondary efficacy endpoints of change from baseline in 6MWD at Week 52, the same nonparametric approach as described in Section 3.13.1.1.2, and the same missing data imputation as described in Section 3.13.1.3, will be utilized.

3.13.2.2. Percent Change from Baseline in Body Weight Loss at Week 52

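### The confirmatory KCCQ-CSS test is valid and powered as stated, but it leaves the baseline score unused and so gives up power that could be had cheaply

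*SAP*

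**What the plan says.** Protocol 9.4.2.1 names the method for change in KCCQ-CSS at Week 52: "a stratified Wilcoxon (Van Elteren) test will be used as the primary analysis method". SAP 3.13.1.1.2 repeats it ("A stratified Wilcoxon test (van Elteren 1960) will be used as the main analysis method, controlling for the stratification factors") and lists the strata: HF decompensation within 12 months, diagnosed T2DM, and BMI below or at least 35 kg/m². A Hodges-Lehmann estimate is reported with it. For 6MWD at Week 52, SAP 3.13.2.1.2 uses "the same nonparametric approach as described in Section 3.13.1.1.2".

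SAP 3.3 sets a general rule that "the baseline value of the endpoint will be used as a covariate when appropriate". Baseline is a covariate in the ANCOVAs for body weight (SAP 3.13.2.2.2) and hsCRP (3.13.2.3.2), in the sensitivity MMRM and ANCOVA for KCCQ-CSS (3.13.1.4), in the sensitivity analyses for 6MWD (3.13.2.4), and in the KCCQ-CSS subgroup ANCOVA (3.15.1).

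On alpha, protocol 9.1 says that "change in KCCQ-CSS will be tested at a 2-sided alpha level of 0.01 in parallel for statistical significance". Alpha may later be recycled to a primary endpoint that fails. Protocol 9.2 claims "roughly 80% power for the change from baseline to Week 52 in KCCQ-CSS using Wilcoxon rank sum test".

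**The concern.** Every participant has a baseline KCCQ-CSS, since change cannot be computed without it. If change depends on the starting score, part of the spread in change is predictable before treatment. A test that ignores this carries the extra spread as noise, and a chance imbalance in baseline passes into the result.

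The initial KCCQ-CSS test is where this would be felt most. It runs at 0.01 with about 80% power, and protocol 9.2 states no allowance for missing data. The baseline-adjusted analyses that the SAP does plan are sensitivity or subgroup analyses, so they cannot rescue the confirmatory test if it narrowly fails.

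**Working it through.** **Inputs** (protocol 9.1 and 9.2): 350 per arm; mean change 10 versus 5, so a difference of 5; SD of change 19 in both arms; two-sided alpha 0.01 (critical value 2.576); Wilcoxon rank sum test on normally distributed change. The efficiency of the Wilcoxon test against the t-test for normal data is 3/π.

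**Step 1: the plan's own figure.** Noncentrality = (5/19) × √(350/2) × √(3/π) = 0.2632 × 13.229 × 0.9772 = 3.402. Power = Φ(3.402 − 2.576) = Φ(0.826) = 79.6%. Noether's formula gives 79.0%, the exact variance under the alternative 79.3%, and the plain two-mean formula 81.7%. The stated figure of roughly 80% reproduces.

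**Step 2: power with baseline adjustment.** Let R² be the share of the variance of change explained by baseline. Adjustment multiplies the SD by √(1 − R²), so power = Φ(3.402/√(1 − R²) − 2.576). R² is not in the documents; every value below is an assumption.

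| R² (assumed) | Noncentrality | Power | Equivalent increase in N, 1/(1 − R²) − 1 | Total N for 80% power |
|---|---|---|---|---|
| 0 | 3.402 | 79.6% | 0% | 708 |
| 0.05 | 3.490 | 82.0% | 5% | 674 |
| 0.10 | 3.586 | 84.4% | 11% | 638 |
| 0.20 | 3.803 | 89.0% | 25% | 566 |
| 0.25 | 3.928 | 91.2% | 33% | 530 |

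If baseline and Week 52 scores have equal variances and correlation ρ, then 1 − R² = (1 + ρ)/2. R² of 0.10 then corresponds to ρ = 0.8, and 0.25 to ρ = 0.5.

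**Step 3: simulation with normal data.** With eight strata of equal expected size and 3,000 runs per setting, van Elteren on change was compared with a stratified rank ANCOVA. Power was 79.2% versus 85.0% at R² = 0.15, 78.8% versus 89.9% at 0.25, and 79.2% versus 94.0% at 0.35. The null rejection rates at R² = 0.25 were 0.8% and 1.0%. A separate simulation of the residual method, unstratified and with 4,000 runs per setting, gave 78% versus 85% at a baseline-change correlation of −0.36 (R² = 0.13) and 80% versus 91% at −0.48 (R² = 0.23).

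**Step 4: simulation nearer to the real data.** The score was bounded at 0 to 100 with baseline at most 80, in eight strata. An assumed 3% of participants died and were imputed from the worst 15% of their own arm, after SAP 3.13.1.3. Van Elteren on change was compared with van Elteren on baseline-adjusted residuals. The last column applies the Step 2 formula from the same starting power. For example, 74.6% implies a noncentrality of 0.662 + 2.576 = 3.238, and Φ(3.238/√(1 − 0.36²) − 2.576) = 81.5%, a gain of 6.9.

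| Correlation of change with baseline (assumed) | Unadjusted | Adjusted | Gain (points) | Gain by formula |
|---|---|---|---|---|
| −0.17 | 73.5% | 74.7% | 1.2 | 1.5 |
| −0.26 | 74.6% | 77.4% | 2.8 | 3.6 |
| −0.36 | 74.6% | 81.1% | 6.5 | 6.9 |
| −0.44 | 73.5% | 83.0% | 9.5 | 10.4 |

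Null rejection was 0.9% unadjusted and 1.1% adjusted. The gain survives bounding and death imputation, slightly reduced. Retrieved-dropout imputation and Rubin pooling were not simulated.

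**Step 5: alpha.** If the full 0.05 came back to KCCQ-CSS by recycling, the unadjusted test would have Φ(3.402 − 1.960) = 92.5% power. That requires the other hypotheses to succeed, and the graph weights are in a figure that is not available here.

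**The case against.** The strongest reply is that nothing is broken. The trial was powered for an unadjusted Wilcoxon test on change, the SAP specifies the stratified version of that test, and the stated power is met. SAP 3.3 asks for the baseline covariate only where appropriate, and a van Elteren test takes no continuous covariate. All of that stands.

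A reader might infer that the primary test breaks a rule the SAP otherwise follows. The documents do not support this. The win ratio and the Week 24 analyses of KCCQ-CSS and 6MWD (Table GPID.3.4) are also unadjusted for the endpoint's own baseline value. The pattern is consistent: parametric models adjust, rank and pairwise methods do not.

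A reader might also take a large gain as established. It is not. No passage gives a baseline-change correlation, and the entry limit of KCCQ-CSS at most 80 at Visit 1 narrows the baseline range. What counts is also the correlation left after the three strata are taken into account. Nor do the lower unadjusted powers in Step 4 show that the trial misses its stated power, because they rest on assumed death rates and score distributions that protocol 9.2 does not use.

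The prespecified ANCOVA and MMRM would show whether baseline imbalance drives the estimate, which partly meets the imbalance worry. They do not add power to the confirmatory test.

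Finally, one might read 6MWD as being tested at 0.01 with a similar loss. Its alpha is whatever the testing graph passes on, and no 6MWD effect size or SD is given.

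**Conclusion.** The confirmatory KCCQ-CSS analysis is valid and consistent with its sample size calculation. Leaving out the baseline score is an avoidable loss of efficiency, not an error. At N=700 and the initial alpha of 0.01, adjustment would add nothing if baseline explains none of the variance of change, about 2 points of power at 5%, about 5 at 10%, about 9 at 20% and about 12 at 25%. Gains are probably somewhat smaller with a bounded score and deaths imputed from the low end. The direction is firm whenever change depends on baseline; the size rests wholly on an assumed R². Recycled alpha would raise the unadjusted power and shrink the benefit. The same reasoning applies to 6MWD at Week 52, without a figure.

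**What to change.** Prespecify one rank-based, baseline-adjusted method in SAP 3.13.1.1.2, SAP 3.13.2.1.2 and protocol 9.4.2.1:

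1. In each imputed dataset, regress change on the baseline score, leaving treatment out of the regression.
2. Apply the van Elteren test and the Hodges-Lehmann estimate to the residuals, with the same three stratification factors.
3. Pool by Rubin's rules, as already planned.
4. Label the estimate as a baseline-adjusted shift.
5. Keep the unadjusted van Elteren test as a sensitivity analysis.

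Stratified rank ANCOVA is a different method, not an equivalent one. It adjusts ranks and does not itself yield a Hodges-Lehmann shift, so the SAP should name a single approach. The residual regression is linear on the raw scale, so a ceiling effect would make it less efficient.

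The data are already collected. The cost is the text change in both documents and a reported shift that is baseline-adjusted; it targets the same quantity as the unadjusted one under a location shift, but may differ otherwise. Make the change before unblinding. Under protocol 9.4.1 it can be justified in the SAP and clinical study report, or needs a protocol amendment if the primary test counts as a principal feature; the sponsor should record which applies.

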3.13.1.2. Occurrence of Cardiovascular Death and/or Heart Failure Event over time

3.13.1.2.1. Time to first occurrence of Cardiovascular Death or Heart Failure Event

3.13.1.2.1.1. Estimand for the Endpoint

The estimand for the primary endpoint is described by the following attributes:

- Endpoint: time from randomization to the first occurrence of the clinical endpoint committee (CEC)-confirmed heart failure events or CV death.
- Treatment condition of interest: tirzepatide MTD versus placebo.
- Handling of ICEs: using treatment policy strategy to handle all ICEs.
- Population: all randomized participants.
- Population-level summary: hazard ratio.

3.13.1.2.1.2. Main Analytical Approach

The primary analysis will be a Cox proportional hazards model with treatment as a fixed effect adjusting for diagnosed T2DM (Y/N), baseline probability of HFpEF ($<0.8, \ge 0.8$), and baseline N-terminal pro b-type natriuretic peptide (NTproBNP) ($<200, \ge 200$ ng/L). The probability of HFpEF is derived from the HFpEF-ABA model (Reddy et al 2024). Participants who did not have an adjudicated primary endpoint event on or prior to the end of follow-up will be censored at the date of participant's end of follow-up. The missing data due to censoring will be implicitly handled by the Cox regression model, assuming censoring is independent of the outcome. The hazard ratio, with its CI and p-value, will be provided through the primary analysis model.

The Kaplan-Meier method will be used to estimate the cumulative event curve over time. Counts and proportions of participants who experience a primary endpoint event will be calculated. The total person-years of follow-up for the primary endpoint, the incidence rate per 100 person-years of follow-up for the primary endpoint, and the absolute risk difference (ARD) for the primary endpoint will be provided.

Person-years of follow-up for a specific event of interest are defined for each participant as the time-to-event divided by 365.25.

The incidence rate per 100 person-years of follow-up is defined by dividing the number of participants who developed the event during the study period by the event specific total person-years of follow-up (that is, time-to-event as defined above) multiplied by 100.

The ARD for an endpoint is defined as the difference in incidence rate per 100 person-years between the 2 treatment groups (placebo minus tirzepatide).

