9.4. Statistical Analyses

9.4.1. General Considerations

Statistical analysis of this study will be the responsibility of sponsor or its designee.

Unless specified otherwise, all tests of treatment effects will be conducted at a 2-sided alpha level of 0.05 and all confidence intervals will be given at a 2-sided 95% level. Efficacy will be assessed using ITT Population and safety will be assessed using the Safety Population.

Any change to the data analysis methods described in the protocol will require an amendment only if it changes a principal feature of the protocol. Any other change to the data analysis methods described in the protocol, and the justification for making the change, will be described in the SAP and the CSR. Additional exploratory analyses of the data will be conducted as deemed appropriate.

The SAP will be completed prior to first unblinding and any subsequent amendments will be documented, with final amendments finalized prior to final database lock. The SAP will include a more technical and detailed description of the statistical analyses described in this section. This section is a summary of the planned statistical analyses of the most important endpoints including primary and key secondary endpoints.

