9.4.2.2. Occurrence of CV Death and/or HF Event over time

The primary analysis model will include fixed factors of treatment and the stratification factors of HF decompensation within 12 months of screening (Y/N), diagnosed T2D (Y/N), and baseline BMI ≥35 kg/m² (Y/N). The analysis model with a full list of covariates will be specified in the SAP. The censoring date for a participant is the date of participant's end of follow-up. The missing data due to censoring will be implicitly handled by the model, assuming censoring is independent of the outcome. The treatment effect estimate, with its 95% CI and p-value, will be provided using the primary analysis model.

The estimated cumulative event curve over time will be provided. Counts and proportions of participants who experience a primary endpoint event will be calculated as well as counts of primary endpoint events. The total person-years of follow-up, the incidence rate per 100 person-years of follow-up, and the absolute risk difference will be provided.

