	Hierarchical composite assessed by win ratio moved to other secondary endpoint.	
	Change from baseline to Week 52 in 6MWD moved to Key Secondary endpoints.	
Section 1.2 Key Secondary Objectives	Key secondary endpoints revised to	To align with protocol (c)
	 change from baseline to Week 52 in 6MWD percent change from baseline to Week 52 in body weight, and change from baseline to Week 52 in hsCRP. 	
	NYHA class, exercise capacity (6MWD at Week 24) moved from Key Secondary endpoints to Other Secondary endpoints.	

Section # and Name	Description of Change	Brief Rationale
Section 3.2 General consideration	Change end of study participation to end of follow-up. Add detail of time to event derivation.	To provide more details of the updated primary analysis and to align with the new primary endpoints.
Section 3.11.1 Study and Study Treatment Exposure	Included longer follow-up interval when summarizing duration.	To provide more details of exposure.
Section 3.11.2 Compliance to Study Treatment	Clarification of compliance criteria.	To align with protocol (c)
Section 3.13.1 Primary Endpoints/Estimands Analysis	Revised statistical methods related to primary endpoints.	To align with the revised primary endpoint and provide an appropriate analysis method for each endpoint/estimand.
Section 3.13.2 Key Secondary Endpoints/Estimands	Revised statistical methods related to key secondary endpoints.	To align with the revised primary endpoint and provide an appropriate analysis method for each endpoint/estimand.
Section 3.13.3 Type I Error Rate Control Strategy for Primary and Key Secondary Efficacy Analyses	Updated type I error rate control strategy	To provide details of the strategy.
Section 3.13.4 Other Secondary	 Other Secondary endpoints added including: hierarchical composite assessed by win ratio clinical outcome events of HF NYHA Class proportion of participants attaining ≥5%, ≥10%, ≥15% and ≥20% in body weight reduction change at Week 52 	To align with the revised primary endpoint and provide an appropriate analysis method for each endpoint/estimand.

Section # and Name	Description of Change	Brief Rationale

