3.13.1.5. Additional Analyses for Composite Endpoint of CV Death And HF Event

The contribution of each component of the primary composite endpoint (HF events and CV death) to the overall treatment effect will be examined. Methods similar to those described for the primary analysis will be used to separately analyze the time from randomization to the first occurrence of each component of the primary composite endpoint. The hazard ratio, with its CI and p-value, will be provided.

The CEC-confirmed total number of HF events (first and recurrent) and CV death will be analyzed by the semi-parametric proportional rates model (abbreviated as the LWYY model)

(Lin et al 2000) with treatment as a fixed effect adjusting for diagnosed T2DM (Y/N), baseline probability of HFpEF ($<0.8, \ge 0.8$), and baseline NTproBNP ($<200, \ge 200$ ng/L). A 30-day spacing rule will be applied when consider recurrent events. If an HF event is followed by another within 30 days, these HF events will be considered as a single HF event and the onset date will be the onset of the first HF event. If an HF event is followed by CV death within 30 days, only the CV death will be considered and the onset date will be the onset of the CV death. If an oral diuretic intensification is within 30 days of the date of randomization, it will not be considered as an endpoint. Participants who did not have an adjudicated primary endpoint event on or prior to end of follow-up will be censored at the date of participant's end of follow-up. The rate ratio with 95 confidence interval and p-value will be provided.

Non-parametric estimates of HF event rates over time, allowing for death as terminal event, will be provided (Ghosh and Lin 2000) with treatment as a fixed effect adjusting for diagnosed T2DM (Y/N), baseline probability of HFpEF ($<0.8, \ge0.8$), and baseline NTproBNP ($<200, \ge200 \text{ ng/L}$). A similar spacing rule, as specified in Section 3.13.1.5, will be applied.

Analyses described in Section 3.13.1.2.1.2 for HF events and CV death will be repeated using the investigator's reported events.

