3.13.2.2.2. Main Analytical Approach

The percent change from baseline in body weight will be analyzed using an analysis of covariance (ANCOVA) analysis. The ANCOVA model will include the categorical effect of treatment, stratification factors excluding baseline BMI group (<35, ≥35 kg/m²), and the continuous covariate of baseline body weight value.

Missing body weight data at the scheduled postbaseline visits will be imputed using the retrieved dropout approach (as described in Section 3.13.1.3) through multiple imputation. The final statistical inference over multiple imputations will be obtained using the method proposed by Rubin (1987).

3.13.2.3. Change from Baseline in High-sensitivity C-reactive Protein at Week 52

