3.13.4. Other Secondary

Unless otherwise specified, other secondary analyses will be guided by the treatment policy strategy using all randomized population. Missing data will not be imputed unless otherwise specified. The other secondary analyses can be seen in Table GPID.3.4.

Table GPID.3.4. Other Secondary

Objectives	Endpoints	Analytical Approaches
Hierarchical	A hierarchical composite of the	The win ratio (Pocock et al. 2012) will be
composite	following:	reported as the measure of treatment effect
_	time to all-cause mortality	based on the principle that each participant is
	through the end of follow-up	compared with every other participant within
	occurrence of HF events	each stratum in a pair-wise manner that
	through end of follow-up,	proceeds in a hierarchical fashion.
	where HF events are as defined	Participants will be stratified according to HF
	in Section 1.1	decompensation within 12 months of
	 number of HF events 	screening (Y/N), diagnosed T2DM (Y/N), and
	• time to first HF events	baseline BMI group (<35 , ≥35 kg/m ²),
	 change from baseline in 	yielding 8 stratification pools. The variance of
	KCCQ-CSS category at Week	win ratio will be calculated by the asymptotic
	52, and	normal U statistic approach (Dong et al.
	Change from baseline in the	2018).
	6MWD category at Week 52.	Missing KCCQ-CSS and 6MWD will be
	The categories for change from baseline	imputed as described in Section 3.13.1.3.
	in the KCCQ-CSS are:	
	1. ≥10-point worsening	
	2. ≥5- but <10-point worsening	
	3. No change (<5-point change)	
	4. ≥5- but <10-point	
	improvement	
	5. ≥10- but <15-point	
	improvement, and	
	6. \geq 15-point improvement.	
	The categories for change from baseline	
	in the 6MWD are:	
	1. ≥30% worsening	
	2. ≥20% and <30% worsening	
	3. \geq 10% and \leq 20% worsening	
	4. no change (<10% change)	
	5. $\geq 10\%$ and $\leq 20\%$ improvement	
	6. $\geq 20\%$ and $\leq 30\%$ improvement,	
	and	
	7. ≥30% improvement.	
Clinical outcome	Time to all-cause death	The time from randomization to the first
events of HF	Time to first occurrence of HF	occurrence of any component of the
	events or all-cause death	composite endpoint will be analyzed by a Cox
	• Time to recurrent events of HF	proportional hazards model similar to the
	events and all-cause death	model described in Section 3.13.1.2.1.2.
	Time to first occurrence of HF	
	events	Time to recurrent event analyses will be
	Time to recurrent events of HF	performed using a LWYY as specified in

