3.15. Subgroup Analyses

3.15.1. Primary Efficacy Endpoints

The following subgroup variables will be considered for subgroup analyses if there are adequate number of participants in each subcategory:

- age group: $<65, \ge 65$
- race: White, American Indian or Alaska Native, Black or African American, Asian, or Other
- sex: Male, Female
- ethnicity: Hispanic or Latino, Not Hispanic or Latino
- region: US, Central/South America, Asia, and Other
- baseline BMI (kg/m²): $<35, \ge 35$
- baseline BMI (kg/m²): $<35, \ge 35$ and $<40, \ge 40$
- HF decompensation within 12 months of screening: Yes, No
- diagnosed T2DM at screening: Yes, No
- atrial fibrillation at baseline: Yes, No
- baseline eGFR (mL/min/1.73m²): $<60, \ge 60$
- N-terminal pro-B-type natriuretic peptide (NT-proBNP) at baseline: <200, ≥200
- NYHA class: Class II, Class III or IV
- baseline use of MRA: Yes, No
- baseline use of RAS inhibitors (ACE +ARB+ARNi): Yes, No
- baseline use of a beta blocker: Yes, No
- baseline use of sodium-glucose co-transporter 2 inhibitors: Yes, No
- baseline use of diuretics: Yes, No
- baseline left ventricular ejection fraction: $<60, \ge 60$
- baseline systolic blood pressure: <130, ≥130
- baseline hsCRP: $<2, \ge 2$
- baseline KCCQ-CSS: <Median, ≥Median
- coronary artery disease at baseline: Yes, No
- baseline heart rate: $<70, \ge 70$
- baseline probability of HFpEF: $<0.8, \ge0.8$, and
- baseline waist-to-height ratio: $<0.6, \ge 0.6$.

Subgroup analyses will be considered for the primary efficacy endpoints. An ANCOVA analysis similar to the model described in Section 3.13.1.4 will be considered for the KCCQ-CSS. A Cox proportional hazards model similar to the model described in Section 3.13.1.2 will be considered for the HF outcomes in each subcategory of the subgroup variable with more than 10 events for the corresponding primary endpoint. In addition, a full model with additional terms of subgroup and subgroup-by-treatment interactions will be used to obtain interaction p-values.

The subgroup analyses may also be performed for the key secondary efficacy endpoints using the primary analysis approaches defined in Section 3.13.2. The same analysis model for the corresponding endpoint will be conducted in each subcategory of the subgroup variable to obtain

estimates of the treatment group difference. In addition, a full model with additional terms of subgroup and subgroup-by-treatment interactions will be used to obtain interaction p-values.

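### The SAP's primary Cox model for CV death or HF events drops two of the three stratification factors that the protocol says it will contain, and does not say so or explain why

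*SAP*

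**What the plan says.** Protocol 6.3 stratifies randomisation by HF decompensation in the previous 12 months, diagnosed T2DM and BMI of at least 35 kg/m². For CV death or HF events, protocol 9.4.2.2 states: "The primary analysis model will include fixed factors of treatment and the stratification factors of HF decompensation within 12 months of screening (Y/N"), followed by T2D and BMI group. Its next sentence leaves the complete covariate list to the SAP.

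SAP 3.13.1.2.1.2 specifies a "Cox proportional hazards model with treatment as a fixed effect adjusting for diagnosed T2DM (Y/N), baseline probability of HFpEF" (below 0.8, or 0.8 and above) and baseline NT-proBNP (below 200, or 200 ng/L and above). T2DM stays. Decompensation and BMI group do not appear.

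Two general rules bear on this. SAP 3.3 adjusts efficacy analyses for the stratification factors by default but allows exceptions where specified. Protocol 9.4.1 says that a change affecting a principal feature needs an amendment, and otherwise: "Any other change to the data analysis methods described in the protocol, and the justification for making the change, will be described in the SAP". The same is due in the CSR.

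The SAP's Major Revision Summary has an entry for Section 3.13.1. It records that the methods for the primary endpoints were revised and gives this reason: "To align with the revised primary endpoint and provide an appropriate analysis method for each endpoint/estimand". Covariates are not mentioned.

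**The concern.** The two documents specify different models for the same primary test. This is the test that holds most of the alpha (0.04 of 0.05), and if it is significant its alpha passes on to the key secondary endpoints. The SAP's model also departs from the randomisation scheme, because two of the three stratification factors are not adjusted for.

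A covariate change in a primary model is legitimate when it is prespecified and explained. Here it is prespecified but not explained, and no analysis shows the result under the covariates the protocol promised. If the p-value falls near 0.04, a reader will ask whether the conclusion depends on the covariate set, and nothing in the plan answers that.

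**Working it through.** **1. The covariate sets side by side**

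| Covariate | Protocol 9.4.2.2 | SAP 3.13.1.2.1.2 |
|---|---|---|
| HF decompensation, 12 months | yes | no |
| T2DM | yes | yes |
| BMI group (35 kg/m²) | yes | no |
| Probability of HFpEF (0.8) | no | yes |
| NT-proBNP (200 ng/L) | no | yes |

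Completing a list of named factors allows additions. It does not obviously allow named factors to be removed. The SAP can state a removal when it means one: the body-weight model in 3.13.2.2.2 uses "stratification factors excluding baseline BMI group". KCCQ-CSS, 6MWD, hsCRP and the win ratio keep all three factors.

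**2. Does any planned analysis use the protocol's set for this endpoint?**

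- The component analyses and the investigator-reported repeat (SAP 3.13.1.5) refer back to the primary method, so they use the reduced set.
- The LWYY and Ghosh-Lin analyses (3.13.1.5) are specified "with treatment as a fixed effect adjusting for diagnosed T2DM (Y/N), baseline probability of HFpEF" and NT-proBNP, the same reduced set.
- The other HF time-to-event endpoints (3.13.4) refer back to these models.
- The subgroup analyses (3.15.1) use "a full model with additional terms of subgroup and subgroup-by-treatment interactions". Decompensation and BMI group are both listed, but one variable enters at a time, on top of the SAP set.
- The win ratio (3.13.4) uses all three factors, "yielding 8 stratification pools", but on a different composite: all-cause death, HF events, KCCQ-CSS and 6MWD.

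None gives the overall treatment effect on CV death or HF events under the protocol's covariates.

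**3. Number of events behind the stated power**

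Protocol 9.2 gives roughly 80% power, two-sided alpha 0.04 and an effect of 0.5, but no event count, so the stated power cannot be reproduced directly. Reading 0.5 as a hazard ratio with 1:1 allocation, Schoenfeld's formula gives

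D = 4(z₀.₉₈ + z₀.₈₀)² / (ln 0.5)² = 4(2.0537 + 0.8416)² / 0.4805 = 4 × 8.383 / 0.4805 ≈ 69.8.

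About 70 events are therefore needed, and 70 events return a power of 0.801. Freedman's formula gives 9 × 8.383 = 75.4, so 76. Neither formula uses covariates, so the change of covariates does not alter this calculation.

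**4. What the change does to the test**

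Each scenario had 5,000 simulated trials at HR 0.5 and 5,000 at HR 1: 700 patients, 1:1 permuted blocks in the 8 strata, and a baseline hazard set to give about 70 events at HR 0.5 (about 91 at HR 1). T2DM prevalence was 45%, inside the 40-50% that protocol 2.2 supposes. The remaining inputs are assumptions, because the documents do not give them:

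- decompensation in 30-50% of patients, rate ratio 1.5-4;
- BMI of at least 35 in 60%;
- NT-proBNP of at least 200 in 45%, rate ratio 2, either independent of decompensation or 30 points more common with it;
- HFpEF probability of at least 0.8 in 50%, rate ratio 1.3;
- rate ratio 1.2 for T2DM and for BMI group;
- follow-up uniform over 1-2.3 years.

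Ranges over seven scenarios:

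| | SAP set | Protocol set | All five |
|---|---|---|---|
| Power at HR 0.5 | 75.7-77.5% | 75.9-78.1% | 76.5-78.6% |
| Type I error, nominal 0.04 | 0.033-0.039 | 0.036-0.042 | not tabulated |

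The SAP set is within 0.9 point of power of the protocol set, in either direction, and loses 0.3-1.4 points against all five covariates. Its model standard error divided by the empirical standard deviation is 0.98-1.02. The SAP and protocol models disagree on significance in 3.2-4.6% of trials at HR 0.5 and 1.1-1.6% at HR 1. The Monte Carlo standard error is about 0.6 point for power and 0.28 point for type I error.

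**The case against.** The strongest reply is that there is no doubt about which model will run. The protocol hands the covariate list to the SAP, SAP 3.3 allows exceptions, and the Cox section specifies one. The model is fixed in advance, so there is no room for a choice after the data are seen. That stands, and it is why this is not a validity problem. It does not supply the justification that protocol 9.4.1 asks for. The CSR must carry the justification too, but that does not relieve the SAP.

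Second, disagreement near the threshold is not peculiar to the SAP's set. In further runs under similar assumptions, the protocol set and the five-covariate set disagreed in 2.3-3.9% of trials at HR 0.5, against 3.4-4.3% for SAP versus protocol. This also stands: the disagreement rate shows that the covariate set can matter near the threshold, not that the SAP's set is worse.

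Third, some related evidence is planned. Decompensation and BMI group are subgroup variables, and the win ratio is stratified by all three factors. This helps a little, but neither gives the overall effect under the protocol's model.

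Fourth, the HFpEF probability might already carry information on BMI. The documents do not list that model's inputs, so this cannot be settled from them. It would be a suitable reason for the SAP to state.

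**Conclusion.** The concern holds. The SAP's primary model omits HF decompensation and BMI group, which the protocol says it will include. The revision log gives only a generic reason that never mentions covariates, and no planned analysis recovers the protocol's model.

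The size is modest. Type I error is not threatened, and the power difference from the protocol model is under one point. The practical exposure is a few percent of trials in which the two models would give different verdicts on an alpha-0.04 primary test. These figures rest on reading the protocol's 0.5 as a hazard ratio, on about 70 events, and on the assumed prevalences and prognostic effects. The textual finding rests on none of them. It is a traceability and consistency defect that should be corrected before unblinding, not a flaw that invalidates the analysis.

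**What to change.** Before unblinding, do one of the following.

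- **Preferred:** add HF decompensation within 12 months (Y/N) and baseline BMI group (<35, ≥35 kg/m²) to the Cox model in SAP 3.13.1.2.1.2 and to the LWYY and other HF-event models in 3.13.1.5, keeping T2DM, HFpEF probability and NT-proBNP. With treatment this makes six parameters on about 70 events, or 70/6 ≈ 12 events per parameter.
- **Alternative:** keep the current set, state in the SAP that the two factors are removed and why, and name the protocol's model (treatment plus all three stratification factors) as a sensitivity analysis for the primary HF outcome.

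The cost is SAP wording plus two binary terms, or one extra model. Both factors are already collected and already used for KCCQ-CSS, 6MWD, hsCRP and the win ratio, so no new data are needed.
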